10.3.7. Other Analyses	39
10.3.8. Interim Analyses	39
11. References	40
12. Appendices	41

List of Tables

Table		Page
Table PRCL 1	Schedule of Activities	12
Table PRCL 2	Objectives and Endpoints.....	16

List of Figures

Figure	Page
Figure PRCL 1 Illustration of study design for Clinical Protocol PRCL-PoC	17

List of Appendices

Appendix		Page
Appendix 1.	Abbreviations	42
Appendix 2.	Clinical Laboratory Tests	44
Appendix 3.	Study Governance Considerations	45
Appendix 4.	Monitoring Tests for Treatment-Emergent Hepatic Abnormality	49
Appendix 5.	Classification of Contraceptive Methods	50

1. Synopsis

Title of Study:

A Phase 2a study to evaluate safety, tolerability, and efficacy of PRCL-02 in patients with moderate to severe chronic plaque psoriasis.

Rationale:

The aim of this study is to evaluate safety, tolerability, and efficacy of PRCL-02 in patients with moderate to severe chronic plaque psoriasis.

Objective(s)/Endpoints:

Objectives	Endpoints
Primary	

 To evaluate the efficacy of PRCL-02 after 12 weeks of once daily oral dosing in patients with moderate to severe chronic plaque psoriasis 	
 A 75% improvement from baseline to Week 12 in the PASI (PASI 75)
Secondary	

 To evaluate the safety and tolerability of PRCL-02 after 12 weeks of once daily oral dosing in patients with moderate to severe chronic plaque psoriasis 	
 Treatment emergent adverse events

 To characterize the pharmacokinetics (PK) of PRCL-02 after multiple once daily oral dosing for 12 weeks, in patients with moderate to severe chronic plaque psoriasis 	
 $AUC_{0-\tau}$, C_{max}, t_{max} at steady state
Exploratory	

 To evaluate clinical response to PRCL-02 over time using the PASI and sPGA 	
 PASI sPGA

 To explore the PK/PD exposure-response relationships of PRCL-02 	
 The relationship between PRCL-02 exposure and selected PD efficacy and/or safety measures may be explored

Abbreviations: $AUC_{0-\tau}$ = area under the concentration versus time curve from time zero to one dosing interval (24 hrs); C_{max} = maximum observed drug concentration; PASI = Psoriasis Area and Severity Index; PD = pharmacodynamics; PK = pharmacokinetics; sPGA = static physician's global assessment; t_{max} = time to reach maximum observed drug concentration.

Summary of Study Design:

This will be a multicenter, randomized, double-blinded, placebo-controlled, multiple oral dose parallel design study of PRCL-02 in patients with moderate to severe chronic plaque psoriasis.

Eligible patients will be randomized to one of 3 arms (2 treatment and 1 placebo) within 28 days following screening. Clinical evaluations are at Day 1, weeks 1, 2, 4, 8, 12, 14, 16, 18 and 20 after randomization.

Efficacy and safety assessments will be performed at each of the study visits. Pre-dose blood samples will be collected between Week 1 and Week 8 to assess achievement of steady state PK, and pre- and post-dose serial samples will be collected at Week 12, 14, 16, 18 and 20 to evaluate steady state PK profile of PRCL-02.

Treatment Arms and Duration:

There will be three parallel treatment arms: 2 dose levels of PRCL-02 and a placebo arm. Patients will be randomized in 1:1:1 ratio to PRCL-02 Dose 1:PRCL-02 Dose 2:Placebo. Study drug will be administered orally once daily for 12 weeks. A loading dose will be implemented for all treatment arms. The highest loading and maintenance doses will not exceed the maximum loading and maintenance doses administered in Part C of the previous study (SMAD) (300 mg and 54 QD respectively).

The planned doses are:

Dose 1: Loading dose of 150 mg followed by a once daily maintenance dose of 25 mg, commencing on Day 2 and continuing for 12 weeks.

Dose 2: Loading dose of 300 mg followed by a once daily maintenance dose of 50 mg, commencing on Day 2 and continuing for 12 weeks.

Doses may be revised upwards or downwards based on new safety information and exposure data becoming available during the course of the study.

Number of Patients:

Approximately 27 patients will be targeted for enrollment in each of the 3 arms of the study (total of approximately 81 patients).

Statistical Analysis:

Efficacy: Efficacy analyses will be conducted on the Intent-to-Treat analysis set. The primary analysis will be conducted using a 1-sided, Fisher's exact test with a 10% type 1 error rate.

Safety: Safety analyses will be conducted on the Safety analysis set. Safety parameters that will be assessed include: adverse events, clinical laboratory parameters, vital signs, electrocardiogram parameters, and physical examination. The parameters will be listed and summarized using standard descriptive statistics.

Pharmacokinetics/Pharmacodynamics: Plasma PRCL-02 PK parameters after multiple dose administration will be calculated using noncompartmental methods. Pharmacokinetic parameters

will be summarized by dose level using descriptive statistics. Mean and individual PRCL-02 plasma concentration-time curves will be represented graphically.

The PK/PD relationship between PRCL-02 exposure and PD efficacy and/or safety measures may be explored.

2. Schedule of Activities

Table PRCL 1 **Schedule of Activities**

Procedure	Screening ^a	1	2	3	4	5	6	7	8	9	FU	EoS ^b
Visit #												
Study Days	-28 to -1	1	8	15	29	57	85	99	113	127		141
Window Period (Days)		±2	±2	±2	±2	±2	±2	±2	±2	±2		±2
Week	-	-	1	2	4	8	12	14	16	18		20
Informed consent	X											
Demographics	X											
Medical history	X											
Inclusion and exclusion criteria	X	X										
Pregnancy test (♀) ^c	X	X	X	X	X	X	X	X	X	X		
Serum FSH (PMP ♀)	X											
QuantiFERON TB Test ^d	X											
HIV/hepatitis screen	X											
Randomization		X										
Study drug dispensing ^e		X	X	X	X	X						
Study drug accountability			X	X	X	X	X					X if ET
Safety Evaluations												
Physical examination ^f	X	X	X	X	X	X	X					X
Height/weight ^g	X	X	X	X	X	X	X					X
Vital signs (pulse and BP) ^h	X	X	X	X	X	X	X	X	X	X		X
12-lead ECG ⁱ	X	X	X	X	X	X	X					X
Clinical laboratory tests ^j	X	X	X	X	X	X	X					X
AE monitoring	X	X	X	X	X	X	X	X	X	X		X
Concomitant medications	X	X	X	X	X	X	X	X	X	X		X
Efficacy and Other Evaluations												
PASI	X	X	X	X	X	X	X	X	X	X		X
sPGA	X	X	X	X	X	X	X	X	X	X		X
PK sampling ^k			X	X	X	X	X	X	X	X		X
Plasma sample collection for PGx assessments		X										

Abbreviations: AE = adverse event; BP = blood pressure; ECG = electrocardiogram; EoS = end-of-study; FSH = follicle stimulating hormone; FU = Follow-up; HIV = human immunodeficiency virus; PGx = pharmacogenomics; PK = pharmacokinetics; PMP = postmenopausal; S = screening; sPGA = static physician's global assessment; TB = tuberculosis.

- ^a Randomization will be within 28 days following the screening visit.
- ^b In the event of early or premature discontinuation, a patient should undergo all activities per the EoS visit.
- ^c Serum pregnancy test at Screening and urine pregnancy test at subsequent visits.
- ^d If the result of the QuantiFERON®-TB Gold test is positive, the patient will be excluded from the study. If result is indeterminate, a single re-test will be allowed. If the result of the second test is positive or still indeterminate, the patient will be excluded from the study. Patients who have been vaccinated with BCG at any time in the past do NOT need to undergo testing. Documentation of previous vaccination is required.
- ^e On days when there is pre-dose PK sampling (at 1 week, 2 weeks, 4 weeks, 8 weeks and 12 weeks after the first dose), the dosing will be at the site after pre-dose sampling (patients will be instructed to not dose at home). The patients will be required to bring to the CRU their study treatment kit with all unused tablets. On all other days, patients should take their medication at approximately the same time in the morning. It is recommended (but not required) that the dose should be taken with food.
- ^f A full physical examination will be conducted at screening and on Week 4. Physical examination must include evaluation of the skin and mucus membranes. A physical examination may be performed at other visits at the investigator's discretion.
- ^g Height at screening visit only.
- ^h Single BP readings and other vital signs (in a seated position) on Day 1 and subsequent visits.
- ⁱ Single 12-lead ECG readings (in supine position, for at least 5 minutes prior to the ECG reading). The screening ECG may be repeated at the investigator's discretion. When scheduled at the same time, the following order of procedures is recommended: ECGs, vital signs, and blood collection (and/or other study procedures).
- ^j Clinical laboratory tests will include hematology, serum chemistry, and urinalysis.
- ^k Pre-dose samples are to be obtained at 1 week, 2 weeks, 4 weeks and 8 weeks weeks after the first dose of study drug. On the last day of dosing (Day 85/Week 12), the following samples are to be collected: pre-dose and 1, 2, 4, 8 hr post last dose. One sample will also be collected on weeks 2, 4, 6 and 8 weeks post last dose. One sample should be taken at the early termination visit, if applicable. Timing of PK sample collection may be adjusted based on clinical needs. Actual sampling dates and times must be accurately recorded.

3. Introduction

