5.1. Overall Design

This is a multicenter, randomized, double-blind, placebo-controlled, parallel design Phase 2a study in patients with moderate to severe chronic plaque psoriasis.

Screening (up to 28 days prior to first dose of study drug) allows for evaluation of inclusion and exclusion criteria. Following Screening, all eligible patients will be randomly assigned (in 1:1:1 ratio) to PRCL-02 Dose 1, PRCL-02 Dose 2, or placebo and will receive study drug for 12 weeks. Following completion of 12-week treatment, all patients will attend Follow-Up Visits at 2, 4, 6 and 8 weeks after the last dose of study drug.

Efficacy and safety assessments will be performed as defined in the Schedule of Activities (Section 2).

Figure PRCL 1 illustrates the study design.

Study governance considerations are described in detail in [Appendix 3](#).

[figure not shown]

Figure PRCL 1

Illustration of study design for Clinical Protocol PRCL-PoC

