7.8. Treatment after the End of the Study

Not applicable.

8. Discontinuation Criteria

Patients discontinuing from the treatment prematurely for any reason should complete adverse event and other follow-up procedures per Section 2 of this protocol.

Patients discontinuing from the study prematurely for any reason must complete adverse event and follow-up procedures per Section 2 of this protocol.

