8.1. Discontinuation from Study Treatment

Discontinuation due to a hepatic event or liver test abnormality. Patients who are discontinued from using study drug due to a hepatic event or liver test abnormality should have additional hepatic safety data collected via EDC. Discontinuation of the study for abnormal liver tests **should be** considered by the investigator when a patient meets one of the following conditions after consultation with the sponsor designated medical monitor:

- ALT or AST >5X ULN
- ALT or AST >3X ULN along with one or more of the following criteria:
 - sustained for more than 2 weeks or
 - TBL >2X ULN or
 - prothrombin time >1.5X ULN or
 - the appearance of fatigue, nausea, vomiting, right upper-quadrant pain or tenderness, fever, rash, and/or eosinophilia (>5%)
- alkaline phosphatase (ALP) >3X ULN
- ALP >2.5X ULN and TBL >2X ULN
- ALP >2.5X ULN with the appearance of fatigue, nausea, vomiting, right quadrant pain or tenderness, fever, rash, and/or eosinophilia (>5%)

In addition, patients will be discontinued from the study drug in the following circumstances:

- White blood cell count $\geq 1.5X$ ULN or an increase in white blood cells above ULN and $>2X$ ULN from last predose measure
- Neutrophil or total lymphocyte count of $\geq 1.5X$ ULN or an increase in neutrophils or total lymphocytes above ULN and $>2X$ ULN from last predose measure
- Patient received concomitant medication listed in Exclusion Criteria
- Patient's failure to comply with protocol requirements or study-related procedures
- Termination of the study by the sponsor or regulatory authorities

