9. SCHEDULE OF ASSESSMENTS

Procedure	Screening									FU	EoS
Visit #	1	2	3	4	5	6	7	8	9	10	11
Study Days	-28 to -1	1	8	15	29	57	85	99	113	127	141
Window Period (Days)		±2	±2	±2	±2	±2	±2	±2	±2	±2	±2
Week	-	-	1	2	4	8	12	14	16	18	20
Informed consent	X										
Demographics	X										
Medical history	X										
Inclusion and exclusion criteria	X	X									
Pregnancy test (♀)	X	X	X	X	X	X	X	X	X	X	
Serum FSH (PMP ♀)	X										
QuantiFERON TB Test		X									
HIV/hepatitis screen	X										
Randomization		X									
Study drug dispensing		X	X	X	X	X					
Study drug accountability			X	X	X	X	X				X if ET
Safety Evaluations											
Physical examination	X	X	X	X	X	X	X				X
Height/weight	X	X	X	X	X	X	X				X
Vital signs (pulse and BP)	X	X	X	X	X	X	X	X	X	X	X
12-lead ECG	X	X	X	X	X	X	X				X
Clinical laboratory tests	X	X	X	X	X	X	X				X
AE monitoring	X	X	X	X	X	X	X	X	X	X	X
Concomitant medications	X	X	X	X	X	X	X	X	X	X	X
Efficacy and Other Evaluations											
PASI	X	X	X	X	X	X	X	X	X	X	X
sPGA	X	X	X	X	X	X	X	X	X	X	X
PK sampling			X	X	X	X	X	X	X	X	X
Plasma sample collection for PGx assessments		X									

See protocol for footnotes.

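### The end-of-study column, which doubles as the early-discontinuation visit, has no pregnancy test in either schedule

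*Protocol*

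**What the plan says.** Table PRCL 1 in Protocol Section 2 marks the pregnancy test at Screening and at Visits 1 to 9, that is to Week 18 (Day 127). The FU and EoS cells of that row are blank. In SAP Section 9 the "Pregnancy test" row is marked at Visits 1 to 10, again to Week 18, and blank at Visit 11 (EoS, Week 20).

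Footnote b gives the EoS column a second use: "In the event of early or premature discontinuation, a patient should undergo all activities per the EoS visit". The drug-accountability row uses it that way, with an 'X if ET' entry. Footnote k also presupposes such a visit: "One sample should be taken at the early termination visit, if applicable".

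Footnote c gives the type of test: "Serum pregnancy test at Screening and urine pregnancy test at subsequent visits". Footnote j describes the laboratory row, which is marked at EoS: "Clinical laboratory tests will include hematology, serum chemistry, and urinalysis".

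Two passages bear on whether an early leaver is seen again. Protocol 5.1: "Following completion of 12-week treatment, all patients will attend Follow-Up Visits at 2, 4, 6 and 8 weeks after the last dose" of study drug. The opening of Protocol Section 8: "Patients discontinuing from the treatment prematurely for any reason should complete adverse event and other follow-up procedures per Section 2 of this protocol". The sentence after it makes the same demand, with 'must', of patients who leave the study.

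**The concern.** The protocol takes exposure in pregnancy seriously. It requires contraception throughout the study (6.1), schedules a test at ten visits, and asks in 9.2.1 that any pregnancy during exposure be reported through the SAE process, with outcomes for mother and fetus. A site that follows the table cell by cell would nevertheless do no pregnancy test when a woman leaves early, although almost everything else is repeated at that visit.

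If that visit is her last, it is also the last scheduled chance to find a pregnancy that began on study drug and to arrange outcome follow-up. This is a patient-safety and scheduling point. The primary PASI 75 comparison is not involved.

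**Working it through.** The plan states no figure on this point, so there is none to reproduce. The check has four parts.

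**1. Is the blank cell real?** In Table PRCL 1 the pregnancy row and the vital-signs row have the same number of cells. Both have ten marks (Screening, Visits 1 to 9) and a blank FU cell; vital signs then has an X at EoS and the pregnancy row does not. In the SAP schedule, vital signs is marked at Visit 11 and the pregnancy test is not. The blank is in the plan and did not arise from a shifted column.

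**2. Is it unusual?** Rows repeated at the dosing visits in Table PRCL 1: pregnancy test, drug dispensing, drug accountability, physical examination, height/weight, vital signs, ECG, laboratory tests, AE monitoring, concomitant medications, PASI, sPGA and PK sampling, 13 in all.
- Marked at EoS: 11 (ten 'X' and one 'X if ET').
- Blank at EoS: 2, namely dispensing, which has no role at exit, and the pregnancy test.

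**3. How much dosing can follow the last scheduled test?** Tests up to the end of dosing fall on Days 1, 8, 15, 29, 57 and 85, so the gaps are 7, 7, 14, 28 and 28 days (sum 84). Doses since the last test, counting the dose on the test day, are

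doses = last-dose day − test day + 1.

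- Largest value at nominal days: last dose Day 56 after a test on Day 29, 56 − 29 + 1 = 28. The same holds for Days 57 to 84.
- With the ±2-day windows: test on Day 27, next visit as late as Day 59, last dose Day 58, 58 − 27 + 1 = 32.
- Average, assuming the last-dose day is spread evenly over Days 1 to 84: each gap g contributes g(g + 1)/2, so (28 + 28 + 105 + 406 + 406)/84 = 973/84 = 11.6 doses.
- More than 14 doses: 14 days in each 28-day gap, 28/84 = 33% of stopping days.

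**4. How many women?** The sample-size sections (Protocol 10.1, SAP 1.3) assume 10% drop-out and 27 patients per arm, so 54 on active drug. The documents give no share of women of childbearing potential; 10 to 30% is assumed.
- Early leavers on active drug: 0.10 × 54 = 5.4.
- Of childbearing potential: 5.4 × 0.10 to 5.4 × 0.30 = 0.5 to 1.6 women. Exposed pregnancies would be a small fraction of these.
- Completers: the last scheduled test is on Day 127, 127 − 85 = 42 days after the last dose. An EoS test would add one more look 141 − 127 = 14 days later.

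**The case against.** The strongest reply is that the harm depends on a reading the protocol does not settle. Footnote b asks for all EoS activities; it does not say that only those are done or that they replace follow-up. Section 8 sends early leavers to the follow-up procedures of Section 2, which could mean the Week 14, 16 and 18 visits, and those carry tests. Against this, 5.1 ties the follow-up visits to completing 12 weeks of treatment. This objection stands in part: undetected exposure is conditional on her not attending those visits. The absence of a test at the exit visit itself is not conditional.

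A second reply is that footnote c names subsequent visits without exception, and that Appendix 2 lists a pregnancy test among the laboratory tests. But footnote c sets the type of test, and Protocol 9.4.3 leaves the timing of the Appendix 2 tests to the Schedule, where the cell is blank. Footnote j limits the laboratory row to hematology, chemistry and urinalysis. Neither closes the gap, although a reader should not infer that footnote c contradicts the table; it is merely ambiguous about EoS.

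Two stronger readings are tempting, and the documents do not support them.
- A reader might infer that the protocol lets a pregnant woman stay on study drug. Pregnancy is missing from the list in 8.1 introduced by "patients will be discontinued from the study drug in the following circumstances" and appears in 8.2 under a stem using 'may'. But that stem also covers the patient's own request and stops for safety, which cannot be optional. The 8.1 list is not complete either, since adverse events in general are absent from it. Nothing suggests that dosing a woman known to be pregnant is intended.
- A reader might infer from 9.2.1 that pregnancies need not be followed after discontinuation, because investigators need not actively seek AEs or SAEs then. The same section says pregnancy is not an AE and requires any pregnancy to be reported separately, so that sentence does not govern it.

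**Conclusion.** The point holds as a narrow scheduling gap. The pregnancy test is the only repeated assessment left out of the early-discontinuation visit, in both schedules. At that visit a woman may be up to 28 doses past her last scheduled test, or 32 at the limits of the windows. An exposed pregnancy could be missed if she has no later visit, and the protocol leaves that open.

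The size is small: roughly 0.5 to 1.6 women on active drug, resting on the planned 10% drop-out and the assumed 10 to 30% share; the 11.6-dose average also rests on evenly spread stopping days. An exit test aids detection and outcome follow-up. It does not prevent exposure, and it could miss a very recent conception. Completers gain little. The change is worth making because it is nearly free, and it has no bearing on efficacy or power.

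**What to change.** Mark a urine pregnancy test as 'X if ET' in the EoS column of Table PRCL 1 and of the SAP Section 9 schedule, matching the drug-accountability row. This works whichever way Section 8 is read.

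Cost: 0.10 × 81 × 0.10 to 0.10 × 81 × 0.30 = 0.8 to 2.4, so about one or two extra urine tests across the trial under the same assumptions. Urinalysis is already part of the laboratory tests at that visit, so no new collection or visit is needed. A full 'X' for everyone would cost 81 × 0.10 to 81 × 0.30, about 8 to 24 tests, for little added value in completers.

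Optionally, one line naming a positive pregnancy test could be added to the drug-stopping list in 8.1. That would be a wording clarification and does not correct a defect. Sample size, analysis and visit count are unchanged.

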3.1. Study Rationale

The aim of this study is to evaluate the safety, tolerability, and efficacy of PRCL-02 in patients with moderate to severe chronic plaque psoriasis. The study will be conducted in compliance with the protocol, good clinical practice (GCP), and applicable regulatory requirements.

3.2. Background

Psoriasis is one of the most common immune-mediated chronic inflammatory skin diseases, affecting about 2- 3% of the world's population. The most common variant is plaque psoriasis (psoriasis vulgaris), which affects most patients with the disease (Nestle et al. 2009; Perera et al. 2012). Psoriasis is associated with a high degree of morbidity; patients have a decreased quality of life (Rapp et al. 1999; Kimball et al. 2008; Lewis-Beck et al. 2013).

Activated T lymphocytes and several of the cytokines they produce are key drivers of pathogenesis in psoriasis. This is supported by the efficacy of several non-biologic (e.g. cyclosporine, Janus kinase inhibitors) and biologic (IL-12/23, IL-17 and TNF α inhibitors) drugs used clinically for treatment of this condition. Current approved treatment options for psoriasis include phototherapy, topical treatments, nonbiologic systemic immune modulators and biologic agents that target various functions of T cells and proinflammatory cytokines. Mild, localized psoriasis is typically treated with topical therapy while more extensive, severe disease often requires systemic, expensive, and potentially harmful treatments. There remains a need for effective treatment options that have superior long-term safety profiles to the current nonbiologic systemic treatments and with a convenient dosing regimen.

Cytoplasmic calcium (Ca $^{2+}$) is an important second messenger in mediating fundamental biological processes in cells (Tian et al. 2016). The Ca $^{2+}$ release-activated Ca $^{2+}$ (CRAC) channel is composed of two key components, STIM (STIM1 and STIM2) (Liou et al. 2005; Zhang et al. 2015) and ORAI or CRACM (ORAI1, 2 and 3; or CRACM1, 2 and 3) (Mignen 2008), with the combination of STIM1/CRACM1 prevailing in most cells and thus best characterized. Antigen stimulation of immune cells triggers Ca $^{2+}$ entry through CRAC channels, promoting the immune response to pathogens by activating the calcineurin-NFAT signaling axis that is targeted by traditional calcineurin inhibitors, such as cyclosporine A and tacrolimus. Recent findings indicated that therapies specifically targeting CRAC channels may serve as improved immunomodulators with high selectivity and low toxicity compared with currently approved immunosuppressive agents.

PRCL-02 is a selective, potent CRACM1 inhibitor which has demonstrated inhibition of T and B cell activation, without any demonstrable effect on other immune cells, and with acceptable safety and tolerability in rats and cynomolgus monkeys after daily oral dosing up to 3 months. Due to the prominent role of T cells in psoriasis, treatment with PRCL-02 in plaque psoriasis is expected to provide clinical benefit with convenient dosing and an attractive safety profile.

